Study protocol and statistical analysis plan

Title:

Detection of deteriorating patients on peripheral surgical wards by an automated notification system

Protocol code: DrePaSiNet

Dresdner Patienten Sicherheits- Netzwerk

ClinicalTrials.gov ID: not yet assigned (by 2018-03-04)

IRB approval: EK DD 291072016

Protocol version: V1.0

Protocol date: 2015-01-01

Responsible Party:

[name]. med. [name] DEAA, MBA

Klinik für Anästhesiologie und Intensivtherapie

Universitätsklinikum Dresden

[name]

[name], Germany

[contact]

Data collection

After approval of the institutional review board (EK DD 291072016) data from four clinical routine databases were collected and analyzed over two 12 months periods. Individual informed consent was waived by the IRB.

On 2016-07-01 a Multiparameter Early Warning Score (MEWS) – based vital monitoring and paging system (Intelligent Guardian Solution (IGS), Phillips, Hamburg, Germany) was deployed on two surgical wards with 56 beds in total. Medical staff received intense training on the handling of the IGS before deployment over two months.

All measurements from the monitors were transmitted via a wireless local area network to a central server connected to the hospital data network and to a paging server (Digitaler Anruf- und Kommunikationsserver (DAKS), Siemens, Erlangen, Germany) for automated notification of the attending surgeon or the MET. All notifications were given via text message on custom DECT phones, including room, and bed number, as well as the present MEWS score and the time over which it changed.

Handling protocol

The handling and escalation/ de-escalation protocol for measurement intervals and devices is displayed in Figure 1.

Text prompts on the spotcheck monitors directly advised the nurses according to the handling protocol. According to the protocol the density of measurements was adapted to the patient's condition. When the MEWS reached 7 or higher the surgical registrar was automatically paged by the system to take care for the deteriorating patient. It was to his discretion to call the MET if necessary. In case of an obviously life threatening condition, the MET could directly be called by a button on the monitor.

[figure not shown]

Figure 1 Flowchart for patient condition- adapted measurement, handling of IGS components, and communication.

Database management

Deployment of the IGS was accompanied by data acquisition in four routine databases from 2016-07-01 to 2017-06-30. The complete year of 2015 served as control period. Data on length of stay, ICU admissions, age, gender, survival, G-DRG- codes and case weight originate from the hospital information system (ORBIS, AGFA HealthCare, Bonn, Germany). Data on comorbidities derive from the anesthesia information system (ANDOK, DATAPEC, Pliezhausen, Germany). The local dataset of the German Resuscitation registry provided all data recorded during the MET missions with or without cardiac arrest. In the intervention phase the IGS database (Philips, Hamburg, Germany) provided all data on MEWS and individual physiologic parameters of all measurements. Aggregation of databases was conducted by use of the key variable “FALLNUMMER” which was part of each dataset.

Statistical analysis

Data are presented as absolute number of patients with respective percentage per group or as parameter mean \pm SD. For comparisons of interval-scaled variables between the observation periods, two tailed, unpaired t-tests were performed. Levene's test was used to check these variables for Gaussian distribution. Nonparametric between group testing was achieved with two tailed Mann-Whitney U- test. Additionally, the chi-square test or Fisher's exact test was applied to nominal-scaled data. To address the fact that patient condition was significantly poorer during the intervention period e.g. in terms of DRG- case weight, comorbidity, and surgical complexity as indicated by duration of surgery, statistical comparisons between the observation intervals were completed regarding the respective G-DRG case weight as a statistical confounder.

SPSS software (IBM SPSS statistics, version 24.0.0.1, Armonk, NY, USA) was used for all calculations. In all statistical comparisons, significance was accepted with an error probability of $p < 0.05$.

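### Ward enters no analysis: a change in the two wards' shares of cases is controlled only as far as case weight captures it, and an effect on one ward alone would not be visible

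*Combined protocol and SAP*

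**What the plan says.** Under Data collection, the system "was deployed on two surgical wards with 56 beds in total", and routine data "were collected and analyzed over two 12 months periods". Beds, cases and specialty are not broken down by ward.

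Under Database management, the intervention period is given by "Deployment of the IGS was accompanied by data acquisition in four routine databases from 2016-07-01 to 2017-06-30" and the comparator by "The complete year of 2015 served as control period". That section does not say that the 2015 cases come from the same two wards. The hospital-system variables are listed as follows: "Data on length of stay, ICU admissions, age, gender, survival, G-DRG- codes and case weight originate from the hospital information system". Ward is not among them.

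Under Statistical analysis, the tests run between periods: "For comparisons of interval-scaled variables between the observation periods, two tailed, unpaired t-tests were performed", with the Mann-Whitney U-test as the nonparametric alternative, and "the chi-square test or Fisher's exact test was applied to nominal-scaled data". The section then says that patients were in worse condition in the intervention period (case weight, comorbidity, length of operation) and that the comparisons therefore took G-DRG case weight into account as a confounder. It does not say how. Ward is not mentioned in this section.

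**The concern.** The system is a ward-level intervention. It works through trained staff, nurses following prompts on the monitors, and a registrar who decides whether to call the emergency team. The quantity of interest is the change within a ward once the system is in place. A comparison over both wards together mixes that change with any change in the wards' shares of cases.

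Two things are at stake:

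- **Ward shares.** If one ward has a higher baseline risk and its share of cases rises or falls, the overall rate moves although nothing has changed on either ward. The direction can favour the system or count against it.
- **Consistency.** There is no concurrent control. Whether both wards moved the same way is the one internal replication the design can offer, and no planned result shows it.

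**Working it through.** The plan states no sample size, event count, event rate or ward split, so it has no figure to reproduce. All rates, splits and case numbers below are assumptions, and none of the calculations includes the case-weight adjustment.

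**1. Shift in the crude rate with no true effect.** Overall rate = w·a + (1 − w)·b, where a and b are the ward risks and w is the share of the ward with risk a.

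| Ward risks | 50:50 | 55:45 | 60:40 | Relative change |
|---|---|---|---|---|
| 6% and 2% | 0.50×6 + 0.50×2 = 4.0% | 0.55×6 + 0.45×2 = 4.2% | 0.60×6 + 0.40×2 = 4.4% | +5%, +10% |
| 5% and 3% | 0.50×5 + 0.50×3 = 4.0% | 0.55×5 + 0.45×3 = 4.1% | 0.60×5 + 0.40×3 = 4.2% | +2.5%, +5% |

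**2. Plausible case numbers.** Cases per year = 56 beds × 365 × occupancy / length of stay. Only the 56 beds come from the plan. Occupancy 0.8 with a 10-day stay gives 20,440 × 0.8 / 10 ≈ 1,635. Occupancy 0.9 with a 5-day stay gives 20,440 × 0.9 / 5 ≈ 3,679. The range used is 1,500 to 3,500 per period.

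**3. False-positive rate of the unadjusted two-sided two-proportion test at 0.05**, for the shifts in step 1:

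| Ward risks | 50:50 to 55:45 | 50:50 to 60:40 |
|---|---|---|
| 6% and 2% | 5.9–7.1% | 8.5–13.3% |
| 5% and 3% | 5.2–5.5% | 5.9–7.1% |

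With equal ward risks it stays at 5.0%, whatever the split.

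**4. Does stratifying by ward correct this component?** Simulation with 2,300 cases per period, the lower-risk ward's share rising from 50% to 60%, no true effect, 20,000 runs:

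| Ward risks | Pooled test | Cochran-Mantel-Haenszel by ward |
|---|---|---|
| 1% and 3% | 7.7% | 4.9% |
| 5% and 10% | 9.9% | 5.1% |
| 5% and 15% | 20.7% | 5.0% |

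**5. Effect on one ward only.** With equal wards and equal baseline risk, a risk ratio of 0.5 on one ward and 1.0 on the other gives a pooled ratio of (0.5 + 1.0)/2 = 0.75. Nothing in the pooled result separates this from a ratio of 0.75 on both wards.

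Power of a ward-by-period interaction on the risk-difference scale, with base rate p and m = half the cases per period, uses z = 0.5p / √{[3p(1 − p) + 0.5p(1 − 0.5p)]/m}. For p = 2% and m = 750, z = 0.01 / √(0.0687/750) ≈ 1.04, which gives 18% power. Over 1,500 to 3,500 cases per period, power is 18–36% at a 2% base rate and 68–96% at 10%.

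**The case against.** The strongest counter-argument is the case-weight adjustment. If the wards differ in risk because their patients differ in severity, a changed split would show in case weight and be at least partly absorbed. This stands in part. The figures in the working are therefore upper illustrations, and because the method of adjustment is not specified, the remainder cannot be sized. The adjustment does not settle the matter, though. Case weight is a case-level variable that need not capture ward differences in staffing or practice, and it cannot reveal an effect confined to one ward.

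Three stronger readings are tempting, and the documents support none of them:

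- A reader might infer that the wards are known to differ in patients, staff or baseline risk. The plan gives only their number, that they are surgical, and their combined beds.
- A reader might take the reported worsening in patient condition as a sign that the ward split changed. Sicker patients on both wards would explain it equally well.
- A reader might assume that ward is already held for every case. It is not in the listed variables. It is probably retrievable, but the plan does not say so.

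The absence of any ward stratification is itself inferred from silence, although nothing in the plan points the other way.

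It is also fair to say that the inflation is small in most of the ICU-admission scenarios, and clear only with 6% and 2% and a ten-point shift in split. Stratifying by ward removes the ward-share component only. Within-ward changes in case mix and confounding by calendar time remain.

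**Conclusion.** The point holds in conditional form and is a worthwhile refinement, not a serious defect. The plan controls a change in ward shares only as far as case weight does, and it would not show an effect limited to one ward.

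Bias needs both a difference in ward risk and a change in split, and the documents report neither. Under the assumed ICU-admission risks, the crude shift is 2.5% to 10% in relative terms. The false-positive rate is between 5.2% and 13.3%, against a nominal 5%, for 1,500 to 3,500 cases per period before case-weight adjustment. The sign is unknown. The visibility point does not depend on these assumptions: as written, no planned result would separate the wards.

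**What to change.** - Confirm that the 2015 control cases come from the same two wards, and retrieve ward for each case in both periods.
- Fit one regression per outcome (logistic for binary outcomes) with period, case weight and ward as a fixed factor. Keep case weight in the model: a Mantel-Haenszel analysis by ward alone would drop control of the one imbalance the plan addresses, so use it only as a supplementary check.
- Report case numbers, outcomes and the period effect with its confidence interval for each ward.
- Show the ward-by-period interaction as descriptive. For rare outcomes its power is low, and testing it for every outcome would add comparisons for which the plan names no multiplicity control.

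The cost is one model term (two with the interaction), one table and the retrieval of ward. Before/after confounding by time is not addressed by this change and should still be stated as a limitation.

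### Mean ± SD is the only planned summary even for variables tested by Mann-Whitney, so the printed effect is not the one tested, and under unequal spread the two can differ in direction

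*Combined protocol and SAP*

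**What the plan says.** All the relevant text is in the combined protocol and SAP.

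- **Presentation** (Statistical analysis): "Data are presented as absolute number of patients with respective percentage per group or as parameter mean" ± SD. No median, quartiles, location shift or confidence interval is planned anywhere.
- **Default test**: "For comparisons of interval-scaled variables between the observation periods, two tailed, unpaired t-tests were performed".
- **Check on those variables**: "Levene's test was used to check these variables for Gaussian distribution".
- **Rank test**: "Nonparametric between group testing was achieved with two tailed Mann-Whitney U- test". No variable is named for it, no rule for switching to it is given, and no effect estimate goes with it.
- **Variables collected** (Database management): "Data on length of stay, ICU admissions, age, gender, survival, G-DRG- codes and case weight originate from the hospital information system".
- **Case mix**: the plan reports that "patient condition was significantly poorer during the intervention period e.g. in terms of DRG- case weight, comorbidity, and surgical complexity", the last of these judged by operating time, and that the comparisons also took G-DRG case weight into account as a confounder.

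The significance level is 0.05 throughout.

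**The concern.** Mann-Whitney responds to whether values from one period tend to exceed values from the other. The difference in means is another quantity. When two distributions have the same shape and differ only by a shift, both have the same sign and the mismatch does little harm. When they are right-skewed and differ in spread, a long tail in one period can raise its mean while most of its values lie lower.

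Under the presentation rule, a table row for a rank-tested variable would show two means, two SDs and a p-value. A reader takes the direction from the means and the significance from the p-value. If ranks and means disagree, that reader would conclude, for instance, that stays became significantly longer when the evidence behind the p-value is that they tended to be shorter. Even without a disagreement, the row gives no estimate of the effect tested and no measure of its precision.

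The check the plan names adds to the worry. Levene's test detects unequal variances. If rejection by it is what sends a variable to Mann-Whitney, which the plan does not say, the rank test would be used where spreads differ, and that is one of the conditions for a reversal.

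**Working it through.** The plan gives no sample size, length-of-stay figure or SD, so there is no figure of its own to reproduce. The check asks whether a significant reversal can happen and what it requires.

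**From the plan:** two-sided tests, significance level 0.05, mean ± SD as the summary.

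**Assumed (none of it in the documents):** log-normal stays rounded to whole days; control median 7 days and log-SD 0.7; intervention median and log-SD varied; 500 or 2,317 cases per period.

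**Formulas**, with median m and log-SD s (subscript 0 control, 1 intervention):

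- mean = m × exp(s²/2)
- SD = mean × √(exp(s²) − 1)
- P(intervention stay > control stay) = Φ[(ln m₁ − ln m₀)/√(s₀² + s₁²)]

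**One case in full** (intervention median 6.5, log-SD 0.9):

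- Control: mean 7 × exp(0.245) = 8.94; SD 8.94 × √(exp(0.49) − 1) = 7.1.
- Intervention: mean 6.5 × exp(0.405) = 9.75; SD 9.75 × √(exp(0.81) − 1) = 10.9.
- Printed mean difference: 9.75 − 8.94 = +0.81 days, so intervention looks longer.
- Rank direction: Φ(−0.0741/√1.30) = Φ(−0.065) = 0.474, below 0.5, so intervention stays tend to be shorter.

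**Condition for the expected means to reverse with these medians:** s₁² must exceed 0.49 + 2 ln(7/6.5) = 0.638, so s₁ must exceed about 0.80.

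**Simulated share of trials with Mann-Whitney p < 0.05 and a mean difference of the opposite sign:**

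| Intervention median | Intervention log-SD | n per period | Expected mean (control 8.94) | P(int > ctl) | Significant reversals |
|---|---|---|---|---|---|
| 6.5 | 0.90 | 2,317 | 9.75 | 0.474 | 86% |
| 6.5 | 0.90 | 500 | 9.75 | 0.474 | 20% |
| 6.5 | 0.80 | 2,317 | 8.95 | 0.472 | 39% |
| 6.5 | 0.75 | 2,317 | 8.61 | 0.471 | 2.5% |
| 6.5 | 0.70 | 2,317 | 8.30 | 0.470 | 0% |
| 7.0 | 0.90 | 2,317 | 10.50 | 0.500 | 2.4% |
| 7.5 | 0.90 | 2,317 | 11.24 | 0.524 | 0% |

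Repeat runs of 500 to 1,000 trials with new random numbers moved these by a few points (83% to 86% in the first row, 39% to 44% in the third).

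A separate set with unrounded stays agrees. With control log-SD 0.8 and intervention median 6.5 with log-SD 0.9, reversals were 1.9%, 13.8% and 40.0% at 300, 1,000 and 2,000 per period. With log-SD 0.8 in both periods they were 0% at every size. Skewness alone is therefore not enough.

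**Levene's test:** in the case worked in full, it rejected in 85% to 100% of trials at 300 to 2,000 per period.

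**The case against.** The strongest reply is that nothing ties length of stay to Mann-Whitney. It is interval-scaled, and the plan's default for such variables is the t-test, which matches mean ± SD. The rank test may be meant for ordinal scores, or only for variables that fail the check. The documents also never say that length of stay is skewed. This stands: the link is a reasonable assumption, not something the plan states. It does not touch the general point, because the presentation rule covers whichever variables get the rank test.

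Second, the plan's account of case mix does not imply the harmful pattern. Sicker patients and more complex surgery suggest longer stays overall, so means and ranks would rise together. The row with median 7.5 gives 0% reversals. A reversal in the direction worked here needs a shorter typical stay and a longer tail at once. This stands too, and it limits how likely a reversal is.

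Third, the case-weight adjustment may mean that the unadjusted rank p-value is not the final basis for conclusions. That is possible, but the plan names no adjusted model and no adjusted estimate, so it does not supply the missing effect.

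Fourth, medians are not what Mann-Whitney tests under unequal spread either. That is correct, and it is why the fix needs a matching effect estimate as well as medians. An SD larger than its mean (10.9 against 9.75) would also alert a careful reader to skew, but would not show which way the ranks point.

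A reader might infer that the p-value itself points the wrong way. A two-sided p-value has no sign. What can conflict is the rank ordering behind it and the printed mean difference.

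**Conclusion.** The point holds in limited form. As written, every variable tested by Mann-Whitney would be summarised by a quantity the test does not assess, with no interval. That follows from the text alone.

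The further risk, a significant result read in the wrong direction, is conditional. It needs a skewed variable to be given the rank test, a different spread in the two periods, and a typical value that moves against the mean. Under the assumptions above it ranged from 0% to 86% of simulated trials, depending mostly on the assumed spread and sample size. No single figure in that range is an estimate for this study.

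Two stronger readings are tempting. One is that length of stay will be misreported; the documents do not say which test it receives or how it is distributed. The other is that a reversal is likely because case mix changed; poorer patient condition does not imply a shorter typical stay with a longer tail. This is a weakness of reporting and interpretation, worth correcting because it can affect the direction of a conclusion and costs almost nothing to remove.

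**What to change.** Name the variables tested by Mann-Whitney. For each one, report median (quartiles) and a rank-based effect with 95% CI: either P(X>Y), preferably with an interval that does not assume equal shapes, or the Hodges-Lehmann difference. Take the direction of the conclusion from that effect. Mean ± SD may stay as extra description.

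If mean stay (bed-days) is the quantity of interest, test it directly and report the mean difference with a Welch or bootstrap 95% CI in place of the rank test.

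The cost is one sentence in the Statistical analysis section and one more table column. No new data are needed.

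### The plan reports poorer patient condition in the intervention period but addresses it through G-DRG case weight alone, giving no reason for that choice and naming no model that adjusts for it

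*Combined protocol and SAP*

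**What the plan says.** The combined protocol and SAP compares calendar year 2015 (control) with 1 July 2016 to 30 June 2017 (intervention). Under Statistical analysis it names the between-period tests. For interval-scaled variables, "two tailed, unpaired t-tests were performed". It adds that "Nonparametric between group testing was achieved with two tailed Mann-Whitney U- test". Nominal data get a chi-square or Fisher's exact test.

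The section then turns to case mix. The reason for the extra step is given as: "To address the fact that patient condition was significantly poorer during the intervention period e.g. in terms of DRG- case weight, comorbidity", followed by "surgical complexity as indicated by duration of surgery". The step itself is that "statistical comparisons between the observation intervals were completed regarding the respective G-DRG case weight as a statistical confounder". Nothing more is said about method.

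Under Database management the sources are listed: "Data on length of stay, ICU admissions, age, gender, survival, G-DRG- codes and case weight originate from the hospital information system"; "Data on comorbidities derive from the anesthesia information system"; and "The local dataset of the German Resuscitation registry provided all data recorded during the MET missions with or without cardiac arrest". All are linked by case number. The source of duration of surgery is not stated.

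**The concern.** The comparison is before-after and not randomised. A difference between the periods can reflect the monitoring system, a change in the patients, or a change in anything else over time. The plan itself reports that the patients changed, and the case-weight step is the only control for case mix that it describes. Two things about that step are open.

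- **Choice of covariate.** Three imbalances are given as examples and one is handled directly. Comorbidity and duration of surgery are covered only as far as case weight tracks them, and the plan does not say why it should.
- **Method.** None of the named tests can hold case weight constant. The wording would fit analysis of covariance, logistic regression, stratification or matching.

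At stake are possible residual confounding of every between-period result, and the reader's ability to check or repeat the adjusted comparison.

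**Working it through.** The plan states no sample size, event rate, effect size or imbalance, so there is no figure of its own to reproduce. The main check is to set the text side by side.

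| Item reported as imbalanced | Source in the plan | Named for adjustment? |
|---|---|---|
| G-DRG case weight | hospital information system | yes |
| Comorbidity | anaesthesia information system | no |
| Duration of surgery | not stated, but evidently available, since its imbalance is reported | no |

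Age and gender are also recorded and are not named for adjustment.

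The text leaves these points about the case-weight step unanswered:

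1. The model. No regression, analysis of covariance, stratified, matched or weighted analysis is named.
2. Whether case weight enters as continuous or in categories.
3. Which outcomes the step applies to.
4. Whether the adjusted or the unadjusted result carries the conclusion.
5. Why case weight is enough for comorbidity and duration.

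**Why point 5 matters (all inputs assumed, none from the documents).** Let outcome Y, true severity U and proxy W each have within-period SD 1. Let corr(Y,U) = b and corr(U,W) = ρ, let U and W both shift by d between periods, and let there be no true period effect. After adjustment for W alone:

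- bias = b·d·(1 − ρ)
- SE ≈ √[(2/n)(1 − (bρ)²)], with n cases per period
- two-sided type I error = Φ(bias/SE − 1.96) + Φ(−bias/SE − 1.96)

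With n = 1000, d = 0.2, b = 0.3:

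| ρ | bias | SE | type I error |
|---|---|---|---|
| 0 (no adjustment) | 0.060 | 0.0447 | 0.269 |
| 0.5 | 0.030 | 0.0442 | 0.104 |
| 0.7 | 0.018 | 0.0437 | 0.070 |
| 1 | 0 | 0.0427 | 0.050 |

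For n from 500 to 2000, d from 0.1 to 0.2 and b from 0.2 to 0.3, the type I error at ρ = 0.5 runs from 0.053 to 0.160, and at ρ = 0.7 from 0.051 to 0.090. Under these assumptions the share of bias left is 1 − ρ. The plan gives no information on ρ, so its step could be almost sufficient or clearly insufficient.

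**Would adding the two covariates help?** In a simulation with assumed inputs (true period OR 1.00, control event rate about 5.5%, shifts of 0.2 SD, uncorrelated comorbidity and duration each recorded with reliability 0.7), the OR was 1.010 to 1.115 with case weight alone and 1.008 to 1.042 with all three covariates, as case-weight reliability fell from 0.94 to 0.31. That advantage is not general. If comorbidity recording is also assumed to drift upward by 0.3 SD between periods, then at case-weight reliability 0.94 the three-covariate OR is 0.973 while case weight alone stays at about 1.01.

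**The case against.** The strongest reply is that the plan does adjust, on one of the three dimensions it lists, and that case weight may carry much of the other two. That stands. A reader might infer that no adjustment was made, or that case weight is a poor proxy and the period effect is biased. The documents support neither: they state an intention to account for case weight, and they contain nothing on how well it tracks comorbidity or duration.

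A second reply is that numerical illustrations say nothing about this trial. That also stands. Every input is assumed, and in the simulation comorbidity and duration are the only causes of the outcome apart from period, so adjusting for them is favoured by construction. A reader might infer that the wider model is always at least as good; the recording-drift example shows that it is not. Nothing in the documents suggests such drift, but nothing excludes it.

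Third, the two periods are each a full 12 months, which balances calendar season. That is a genuine design feature, but it does not address case mix or longer-term trend.

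Fourth, the plan is written in the past tense and already reports the imbalances, so a model added now cannot count as prespecified. This is correct, and it limits the rank such a model can claim.

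The replies do not remove two facts visible in the text: no adjusting model is named, and no reason is given for relying on case weight alone.

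**Conclusion.** The point holds as a cheap improvement, not as a demonstrated error. It is more than a request for detail: the plan identifies comorbidity and duration of surgery as imbalanced, comorbidity is in a listed and linked database, duration was evidently to hand, and neither is used. Residual confounding of the period effect is possible. Its size and direction cannot be derived from the documents; the illustrations show only that the answer depends on how closely case weight tracks severity.

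The absence of a named model rests on the text alone and needs no assumption. The claim that more covariates would reduce bias is conditional on their being recorded reasonably well and alike in both periods.

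**What to change.** **Model.** For each outcome, report one regression on period: logistic for death, ICU admission and cardiac arrest, penalised if events are few, and log-linear or similar for length of stay. Adjust for G-DRG case weight, comorbidity and duration of surgery, plus age and gender where events allow. Give the adjusted period effect with its 95% CI.

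**Standing.** Show it beside the same regression with case weight as the only covariate. Label it post hoc if it was added after the imbalances were seen. Treat the unadjusted tests as descriptive. If the two adjusted results differ, draw the conclusion with caution.

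**Cases without surgery or an anaesthesia record.** Keep all cases in the model. For non-operated cases duration is undefined, not missing, so use an operated/not-operated indicator with duration set to zero. Use multiple imputation where comorbidity or duration is truly missing. Report the number of cases without an anaesthesia record by period, and add a complete-case sensitivity analysis.

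**Statements to add.** Give the source of duration of surgery. State that differences in comorbidity recording and calendar-time differences between 2015 and 2016/17 may remain.

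**Cost.** Revised wording and some further model runs. Age, gender, case weight and comorbidity are in the linked databases, so no new data collection is evident, subject to confirming where duration comes from. The downsides are some missing covariate data, a limit on covariates when events are few, and no guarantee that bias is removed.

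### The only named adjuster, G-DRG case weight, may already contain care given for deterioration; if so, adjusting for it can make an ineffective alert system look protective against events such as ICU admission

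*Combined protocol and SAP*

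**What the plan says.** The Statistical analysis section gives its reason for adjusting: "patient condition was significantly poorer during the intervention period e.g. in terms of DRG- case weight, comorbidity, and surgical complexity", the last item being "surgical complexity as indicated by duration of surgery". Its remedy is that "statistical comparisons between the observation intervals were completed regarding the respective G-DRG case weight as a statistical confounder". It does not say what model this means, and it names no other covariate.

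The Database management section gives the source of the weight: "Data on length of stay, ICU admissions, age, gender, survival, G-DRG- codes and case weight originate from the hospital information system". It adds: "Data on comorbidities derive from the anesthesia information system". Neither section defines case weight or says when in the stay it is fixed.

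The comparison is with a historical control: "The complete year of 2015 served as control period", against "data acquisition in four routine databases from 2016-07-01 to 2017-06-30". The Handling protocol section describes how the system acts on care during the stay: "When the MEWS reached 7 or higher the surgical registrar was automatically paged by the system to take care for the deteriorating patient".

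**The concern.** The issue is timing, not the number of covariates. A confounder has to be settled before the exposure can act. The plan treats case weight as a measure of how ill patients were, but lists it beside length of stay, ICU admissions and survival, which describe the whole stay. Suppose the weight is built from the codes of the completed stay. Then, of two patients alike on reaching the ward, the one who deteriorates and goes to the ICU can end with the higher weight. The alert system exists to change that course. Comparing periods at equal case weight would then match patients partly on the event being counted.

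The direction matters. At a given case weight, a patient with an event has part of the weight explained by the event and so tends to have been less ill at baseline. If intervention patients are sicker on average, the adjustment credits them with too much expected risk, and an inert system can look protective. Adding covariates while case weight stays in the model would not in general remove this.

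**Working it through.** The plan states no event rate, sample size or adjusted estimate, so there is no figure to reproduce. The check is whether the mechanism can matter, under stated assumptions.

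**Taken from the document:** case weight is the sole named adjuster; intervention patients were sicker; the system acts during the stay.

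**Assumed:**
- Baseline severity S has SD 1 and is shifted by δ = 0.2 in the intervention period.
- Event: logit = −2.5 + 0.7·S + log(true OR)·period, so β = 0.7 (about 8–10% with an event).
- Case weight = 3 + S + k·event + noise with SD 0.5. Here k is what an event adds to the weight, in SDs of baseline severity; k = 0 means a pure baseline measure.

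**Approximation.** For fairly rare events and normal severity, with R² the share of case-weight variance due to severity (within period and event status):

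log OR (case-weight-adjusted) ≈ log(true OR) + δβ(1 − R²) − δkR²

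The second term is ordinary residual confounding from an imperfect proxy. The third is the post-exposure part. With R² = 1/(1 + 0.25) = 0.80:
- residual confounding: 0.2 × 0.7 × 0.2 = 0.028
- post-exposure part: 0.2 × 0.8 × k = 0.16k
- unadjusted error: 0.2 × 0.7 = 0.14, OR e^0.14 = 1.15

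**System with no effect (true OR 1.00):**

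| k | 0.028 − 0.16k | OR, formula | OR, simulated (600,000 stays) |
|---|---|---|---|
| 0 | +0.028 | 1.03 | 1.02 |
| 0.5 | −0.052 | 0.95 | 0.94 |
| 1 | −0.132 | 0.88 | 0.87 |
| 2 | −0.292 | 0.75 | 0.75 |

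The simulated unadjusted OR is 1.14. Adjusting for true baseline severity gives 0.99 to 1.02. Other runs, of 300,000 to 1,000,000 stays, differ by at most about 0.03.

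**A differently built model.** ICU-type treatment has logit −2.2 + S; log case weight = 0.5·S + b·treatment + noise with SD 0.4; the shift is 0.2 SD and there is no effect. The case-weight-adjusted OR for ICU treatment was 1.09, 0.96 and 0.83 at b = 0, 0.5 and 1.0, against 0.98 to 1.01 adjusted for severity. In the same model, death did not feed the weight. With no effect on death, its case-weight-adjusted OR stayed at 1.09 to 1.11, against 1.22 to 1.23 unadjusted. The artefact therefore attaches most clearly to outcomes that themselves raise the weight.

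**When it disappears.** With δ = 0 and an inert system, both error terms vanish. The simulation agrees: ORs were about 1 for every b.

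**Length of stay** (true OR 0.70; LOS = 8 + 2·S + 5·event + noise with SD 4). Adjusting for severity gives about −0.14 days. Adjusting for case weight gives −0.06 at k = 0 and −0.05 at k = 1. Most of the shrinkage is present when the weight contains no treatment, so it is proxy noise. Only k = 2 (about +0.02) shows a further move.

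**Would realistic baseline variables do better?** If they explain 30–50% of severity, the error in a null system is 0.14 × (1 − R²):
- 30%: 0.098, OR 1.10
- 50%: 0.070, OR 1.07

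Simulation gives 1.07 to 1.10. Case weight has the larger error in size once 0.16k − 0.028 exceeds these values:
- 50% proxies: k above (0.070 + 0.028)/0.16 = 0.61
- 30% proxies: k above (0.098 + 0.028)/0.16 = 0.79
- no adjustment: k above (0.14 + 0.028)/0.16 = 1.05

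**The case against.** The strongest objection is that the key premise is not written down. The plan does not say that the weight is fixed at discharge or includes ICU care. This stands, and the point is therefore conditional.

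Second, case weight may be better than the alternatives. For k up to about 1 it is nearer the truth than no adjustment, and for small k it beats baseline variables that explain only 30–50% of severity. For length of stay those variables gave +0.08 to +0.20 days, the wrong sign, and were worse than case weight at every k tested. This also stands. It is why the fix is confined to event outcomes and keeps the case-weight result in view. It does not rescue case weight as the sole adjuster for events: the errors differ in direction. Incomplete baseline adjustment leaves sicker intervention patients looking worse, against the system, while case weight with enough post-exposure content favours it.

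Third, the availability of duration of surgery is uncertain. The plan cites it without a source, and the duration of a reoperation would itself be post-exposure. That stands and limits which operation can be used.

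A reader might also infer that the trial's whole conclusion rests on the case-weight comparison. The plan names no primary outcome or primary analysis and lists unadjusted tests as well, so that inference is not supported.

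**Conclusion.** The concern holds in conditional form and should be fixed. If case weight reflects the coded stay, and ICU care or complications raise it, the plan as written conditions event outcomes on something the alert system can change. Given the severity difference the plan reports, an inert system could then show an OR of roughly 0.94 to 0.75 for k between 0.5 and 2. The values of k, the 0.2 SD shift and the noise are assumptions. The direction of the shift comes from the plan and does not rest on case weight alone, since comorbidity and duration of surgery also differed.

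Three stronger readings are not supported. The documents do not show that this trial's comparison is biased, or by how much, because k and the timing of the weight are unknown. They do not show that length of stay is distorted by post-exposure content. Nor does it follow that no adjustment would be better: under the assumed shift, the unadjusted OR for an inert system is 1.14.

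**What to change.** - State how case weight is defined and when it is fixed. If it was fixed at admission, say so; the point is then closed.
- Otherwise, for event outcomes, make the main between-period comparison a specified regression adjusted for variables settled before ward exposure: age, gender, comorbidities and, where recorded, duration of the operation preceding ward monitoring.
- Report the unadjusted and case-weight-adjusted results beside it, the latter labelled as conditioning on a possibly post-exposure variable.
- Draw a conclusion only where the analyses agree.

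The cost is a change of wording and a small re-analysis. Age, gender and comorbidities are already held in databases linked by case number; the source of duration of surgery has to be stated. Cases without an anesthesia record will lack comorbidity data and need a stated rule, such as a separate category. Residual confounding will remain because the baseline variables capture severity only in part, and the report should say that this error runs against the system.
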